A Novel Negative Pressure Isolation Device Reduces Aerosol Exposure: A Randomized Controlled Trial

Study Protocol and Statistical Analysis Plan

Trial Registration: ClinicalTrials.gov, NCT 04864236

June 28, 2021

Principal Investigator:

[name]

[contact]

UCLA Department of Anesthesiology and Perioperative Medicine, [name]

Inclusion criteria:

Adult patients (age>18) undergoing elective surgery requiring general endotracheal anesthesia

Exclusion criteria:

Patients with BMI > 40 kg/m², or

Patients predicted to be difficult mask ventilation or intubation (as determined by anesthesiologist), or

Patients refusing to consent for any reason (ie. claustrophobia or inability to cooperate).

Preoperative:

Patients will be screened and identified by the study team and allocated to each group via simple randomization (1:1), which will occur as soon as the OR schedule is available for viewing.

Patients will be randomized to either device or no device. The study investigator will obtain consent the day of surgery. Also at the time of randomization, the anesthesia providers involved will be informed and asked to review the study protocol. Only the study investigators will be involved in the use of the device during patient care.

On the day of surgery, the primary anesthesia provider will be provided with the unassembled device (if assigned to the device group) and be asked to assemble it. This process will be observed and timed by a study coordinator.

Intubation:

For device group: one of the study investigators will place the device around the patient's head. At this time, one particle counter will be positioned on an IV pole next to the study investigator at the level of his/her nose. A second particle counter will be positioned next to the patient's head in order to take measurements from inside of the device. The study team will obtain baseline measurements from both inside and outside the device simultaneously. At the start of preoxygenation (routine part of anesthesia), the study team will begin nebulizing 5ml of saline using a standard nebulizer at 5 liters per minute of oxygen flow. A study team member will be holding the nebulizer close to the patient's nose and mouth. This will simulate airborne contamination that is generated by the patient. During this process, the patient will be instructed to breathe normally for 1 minute, then breathe deeply for 1 minute, and then breathe normally again for 1 minute. During intubation (routine part of anesthesia), the nebulizer will be placed next to the patient's head and it will be kept on until after the patient has been intubated.

Concurrent with the start of preoxygenation, the particle counter will start measuring particle counts. 1 minute after the endotracheal tube or laryngeal mask airway is secured, the anesthesia provider will be instructed to remove the device. A study coordinator will record particle counts continuously until 2 minutes after the device is removed from around the patient's head.

For no device group: exactly the same except no device will be placed around patient's head.

Digital recordings of the particle counts and distribution of particle sizes will be recorded during the conduct of the study in the operating room. These recordings will not be stored with any personally identifiable information. These recordings will be stored on a secure laptop

(university-owned and encrypted) that is accessible only to the study investigators. If the participant decides to withdraw from the study, the study investigators will destroy the recordings immediately.

Statistical Methods:

Primary outcome: particle count measurements during intubation

Statistical analysis plan:

Particle counts will be compared between groups (device vs no device) using an independent samples t-test (or Wilcoxon Rank Sum Test if distributional assumptions are violated).

Power/sample size:

- 1) From a statistical perspective, a sample size of 10 per group allows us to detect an effect size as small as 1.35 between groups (using a t-test, >80% power, two sided alpha 0.05). A similar study (17) exploring the effectiveness of several different containment devices on airborne particles in similar settings mentioned an effect size of 1.0 (20,000 particles vs 12,000, SD of 8,000). We hypothesize that our device will be more effective than any device tested in this previous study at reducing airborne contamination so this is a conservative estimate of what we expect to see with our device.
- 2) Ultimately, we envision a final sample size of 50 per group to better assess both efficacy of the primary outcome as well as increase reliability in our secondary outcomes. This sample size will allow us to detect effect sizes as low as 0.57 between groups (using a t-test, >80% power, two sided alpha 0.05) and gives us a measure of precision of a confidence interval for the mean on our primary outcome of within +/-2,273 particles assuming the box group is 12,000 with a SD of 8,000.(17)

Secondary outcomes:

time to intubation (defined as time from the first entry of laryngoscope into pt's oropharynx to the time of confirmed successful tracheal intubation),
total number of intubation attempts,
pre-op airway assessment (Mallampati score and thyromental distance),
laryngoscopy grade view (Cormack-Lehane) obtained during intubation

Analysis plan:

Secondary outcomes will be compared between groups (where possible) using an independent samples t-test (or chi-square test) as appropriate.

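### Patients are allocated from the operating-room schedule before day-of-surgery consent, with no concealment described, so refusals and possibly airway exclusions fall after allocation

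*Combined protocol and SAP*

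**What the plan says.** The order of events is under the Preoperative heading. Selection and allocation share one sentence: "Patients will be screened and identified by the study team", who are then "allocated to each group via simple randomization (1:1), which will occur as soon as the OR schedule is available for viewing". Consent comes later: "The study investigator will obtain consent the day of surgery".

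Two exclusion criteria matter here. One is refusal, worded as "Patients refusing to consent for any reason (ie. claustrophobia or inability to cooperate". The other is discretionary: "Patients predicted to be difficult mask ventilation or intubation (as determined by anesthesiologist), or". No time is given for that airway judgement.

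On who knows what and when, the plan says: "Also at the time of randomization, the anesthesia providers involved will be informed and asked to review the study protocol". It does not say whether that information includes the arm. The assembly step comes later, on the operating day: "the primary anesthesia provider will be provided with the unassembled device (if assigned to the device group) and be asked to assemble it". From then on that provider knows the arm.

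The secondary outcomes include "time to intubation (defined as time from the first entry of laryngoscope into" the oropharynx to confirmed tracheal intubation, number of attempts, Cormack-Lehane view, and a pre-operative airway assessment (Mallampati, thyromental distance). All are to be compared between groups without adjustment. The document describes no concealment, analysis population, or way of counting and reporting patients lost after allocation.

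**The concern.** Randomisation protects a comparison only if nothing related to the arm decides who stays in after allocation. Here two steps can remove patients after the arm is set.

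- **Refusal.** This is certain to fall after allocation. The plan's own example, claustrophobia, is a reason that could depend on the arm in a trial of a device placed around the head. A study investigator obtains consent, and nothing stops that person from knowing the arm.
- **Airway exclusion.** This may fall after allocation. If the provider who has been handed the device makes the judgement, it is made with the arm known.

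The second route matters more for results, because predicted airway difficulty bears directly on intubation time, attempts and view. If more predicted-difficult airways are dropped from the device arm, the device looks too favourable on these outcomes. The documents give no reason to expect refusals alone to shift them. The primary particle count is less exposed because the aerosol comes mainly from a nebuliser. Since losses by arm are not to be reported, a reader could not tell afterwards whether selection had occurred.

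**Working it through.** **The plan's own figures.** From Power/sample size, with a two-sample t-test (noncentral t, two-sided alpha 0.05): 10 per group at 1.35 SD gives 81.4% power, and 50 per group at 0.57 SD gives 80.6%. The stated precision is t(0.975, 49) × 8,000/√50 = 2,273.6. All three agree with the plan. Neither sample size allows for losses after allocation.

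**Inputs for the bias.** Group size (50 or 10) and SD (8,000 particles) come from the plan. Loss rates, leaver differences and correlations are not in the documents and are assumed, with ranges starting at zero. The control arm is assumed to lose no one.

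**Step 1: any differential loss.** Shift in SD = (extra device-arm loss) × (leaver minus stayer difference in SD). The false-positive rate is the probability that a t-test with n1 device and n0 control patients rejects when the only difference is this shift, with noncentrality = shift/√(1/n1 + 1/n0). For 40 vs 50 and leavers 1 SD worse, the shift is 0.20 × 1 = 0.20 and the noncentrality is 0.20/√(1/40 + 1/50) = 0.943.

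| Device vs control | Leaver difference (SD) | Shift (SD) | False-positive rate |
|---|---|---|---|
| any | 0 | 0 | 5.0% |
| 48 vs 50 (about 5% lost) | 0.5 | 0.025 | 5.2% |
| 48 vs 50 (about 5% lost) | 1.0 | 0.05 | 5.7% |
| 45 vs 50 (10% lost) | 0.5 | 0.05 | 5.7% |
| 45 vs 50 (10% lost) | 1.0 | 0.10 | 7.7% |
| 40 vs 50 (20% lost) | 0.5 | 0.10 | 7.5% |
| 40 vs 50 (20% lost) | 1.0 | 0.20 | 15.4% |
| 8 vs 10 (20% lost) | 1.0 | 0.20 | 6.8% |

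For scale, the 95% CI half-width for the group difference at 40 vs 50 is 0.42 SD, so the largest shift is about half of it (0.20/0.42 = 0.48).

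**Step 2: airway exclusion alone.** Treat predicted difficulty as standard normal and remove the hardest fraction p from the device arm only. The arm's mean difficulty falls by φ(c)/(1 − p), where c is the (1 − p) quantile: 0.1031/0.95 = 0.109, 0.1755/0.90 = 0.195 and 0.2800/0.80 = 0.350 SD for p = 5%, 10% and 20%. The outcome shift is the correlation ρ between prediction and outcome times that value. Error rates are from simulation (100,000 trials, t-test):

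| Excluded, device arm only | ρ = 0 | ρ = 0.3 | ρ = 0.5 |
|---|---|---|---|
| 5% | 5.0% | 5.2% | 5.8% |
| 10% | 5.0% | 5.9% | 7.6% |
| 20% | 5.0% | 7.8% | 13.1% |

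**Step 3: would the planned airway comparison catch it?** In the same model, this is the chance that a 5%-level test on a pre-operative airway measure is significant, by that measure's correlation with the prediction:

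| Excluded | 0.5 | 0.7 | 1.0 |
|---|---|---|---|
| 5% | 5.8% | 6.5% | 8.3% |
| 10% | 7.6% | 10.3% | 16.5% |
| 20% | 13.0% | 21.7% | 43.4% |

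The measure is treated as continuous, although Mallampati is ordinal.

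**Step 4: primary outcome.** With leavers differing by 0 to 0.25 SD in particle count and up to 20% extra loss, the shift is at most 0.20 × 0.25 = 0.05 SD, or 0.05 × 8,000 = 400 particles. The error rate is 5.0% to 5.6%. The plan's reference effect is 1.0 SD.

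**The case against.** The strongest reply is that the certain route has no shown effect and the harmful route is not certain. Only refusals are fixed by the text as coming after allocation, and nothing suggests that refusers differ in ease of intubation. The sentence that names screening before allocation can fairly be read as placing the airway exclusion first. Bias by that route needs a late judgement, knowledge of the arm, and a different threshold by arm. None of these is stated. That stands, and it is why the size may be zero. It does not remove the ambiguity: the text permits a late judgement made with the arm known.

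A second point is that the upper figures are corner cases. The 15.4% needs 20 points of extra loss and leavers a full SD worse. The 13.1% needs exclusions from one arm only, under a criterion that applies to both. If 20% of device and 10% of control patients are excluded, the shift is ρ × (0.350 − 0.195), or 0.05 to 0.08 SD for ρ of 0.3 to 0.5, and the error rate at 40 vs 45 is about 5.5% to 6.4%. Equal exclusion gives 5.0%. This is correct and lies within the stated range; the upper ends are bounds, not expectations.

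Third, a false-positive rate in this direction is almost wholly a false finding that the device makes intubation easier. If the worry is that the device hinders intubation, the relevant error is a missed slowing, which is not quantified here. An SD shift also only approximates what happens to attempts and Cormack-Lehane grade. Both points stand as limits on the figures. The same shift would offset a real slowing by the same amount.

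Finally, the primary outcome is barely touched. That is agreed.

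**Conclusion.** The concern holds. The stated order of events puts every refusal after allocation, leaves the timing of a discretionary airway exclusion open, and describes neither concealment nor the handling of later losses. It should be fixed, mainly for the sake of the secondary intubation outcomes, whose reliability is one of the plan's stated reasons for going to 50 per group.

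The size is unknown. Over the assumed ranges the false-positive rate on an intubation outcome is 5.0% to 15.4% for general differential loss and 5.0% to 13.1% for airway exclusion alone, and it stays at 5.0% if losses are alike in both arms or unrelated to the outcome. The planned comparison of Mallampati score and thyromental distance is only a partial safeguard, since it would often miss an imbalance of the size considered. Confidence is medium: the sequence is explicit, but its consequence rests on inputs that the documents do not supply.

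**What to change.** Reorder the preoperative steps:

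1. Screen from the operating-room schedule and tell providers about the trial without naming an arm.
2. On the day of surgery, obtain consent, then record the anesthesiologist's eligibility judgement and the pre-operative airway assessment.
3. Only then release a concealed 1:1 allocation, by sealed opaque envelope or web system.
4. Analyse all randomised patients who have data in their assigned arm, and report losses after randomisation by arm with reasons.

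Patients who refuse would then never be randomised, so the data they cannot supply no longer affect the comparison.

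The cost is a concealed list and a changed day-of-surgery workflow, with no extra patients. A device must be on hand for every consented case. Providers would learn the arm later, so the timed assembly has to fit between allocation and induction. They can still review the protocol in advance.

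### Eligibility and procedure name different airways, and time to intubation has no value for a patient who is never tracheally intubated

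*Combined protocol and SAP*

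**What the plan says.** All references are to the combined protocol and SAP.

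- **Inclusion criteria:** "Adult patients (age>18) undergoing elective surgery requiring general endotracheal anesthesia". No laryngeal mask population is named. The Exclusion criteria remove patients in whom the anesthesiologist predicts difficult mask ventilation or intubation.
- **Intubation section:** the device comes off "1 minute after the endotracheal tube or laryngeal mask airway is secured", and recording continues until 2 minutes after removal. Of the nebulizer the same section says "it will be kept on until after the patient has been intubated", with no equivalent for a laryngeal mask.
- **Statistical Methods:** "Primary outcome: particle count measurements during intubation".
- **Secondary outcomes:** time to intubation runs from first laryngoscope entry "to the time of confirmed successful tracheal intubation". The list also includes "total number of intubation attempts" and the Cormack-Lehane grade.
- **Analysis plan for secondary outcomes:** groups are compared, where this is possible, by t-test or chi-square test. Nothing is said about patients without an end time. The rank-sum alternative is offered for particle counts, not for secondary outcomes.

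**The concern.** There are two problems, and they are separate.

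The first is consistency. Eligibility rests on an endotracheal airway, device removal on either of two airways, and the nebulizer and the primary outcome on intubation. For a patient whose airway ends as a laryngeal mask, the text gives an event for removing the device but none for stopping the aerosol source. The source and the measurement period both bear on the particle count.

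The second is the definition of time to intubation. It exists only for patients in whom tracheal intubation succeeded. A patient in whom it never succeeds would be among the slowest, yet has no number for a t-test to use. If such patients are simply left out and occur more often in one arm, that arm looks faster than it was. The device surrounds the head during laryngoscopy, so unequal failure between the arms cannot be ruled out in advance.

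**Working it through.** **Step 1. The events set side by side.**

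| Item | Stated end event | Patient with a tracheal tube | Patient ending with a laryngeal mask |
|---|---|---|---|
| Eligibility | Endotracheal anesthesia required | Met | Not met if the mask was planned; met if it followed failed intubation |
| Device removal | Tube or mask secured, plus 1 minute | Defined | Defined |
| End of recording | Device removal plus 2 minutes | Defined | Defined |
| Nebulizer off | After intubation | Defined | No stated event |
| Time to intubation | Confirmed tracheal intubation | Defined | No end time |
| Number of attempts | None needed | Countable | Countable if intubation was tried |

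The rows agree for a tube and part company for a mask. A failed first attempt followed by a successful one keeps its full time, because the clock starts at the first laryngoscope entry. Only patients never tracheally intubated lack a value.

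**Step 2. The plan's own figure, and whether power is the issue.** The plan gives no failure rate and no mean or SD for time to intubation. Its only power statement at the final size is an effect size of 0.57 with 50 per group, two-sided alpha 0.05 and more than 80% power, written for the primary outcome. The noncentrality is 0.57 × √(50/2) = 2.85 on 98 degrees of freedom, which gives 80.6% power, so the figure reproduces. For a standardised effect of the same size with patients lost from one arm, the noncentrality is 0.57/√(1/n₁ + 1/50):

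- n₁ = 49: power 80.2%
- n₁ = 48: power 79.7%
- n₁ = 47: power 79.3%

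Loss of power is negligible. What matters is which values are lost.

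**Step 3. Size of the bias, on assumed figures.** Assume a mean of 30 s among intubated patients, and count each failure at 120 s. With f failures among 50 patients, the arm mean with everyone counted is [(50 − f) × 30 + f × 120]/50, against 30 s when failures are left out. The difference is f × 90/50 = 1.8f seconds.

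| f | Mean with failures counted | Understatement | Relative to 30 s |
|---|---|---|---|
| 0 | 30.0 s | 0 s | 0% |
| 1 | (1,470 + 120)/50 = 31.8 s | 1.8 s | 6% |
| 2 | (1,440 + 240)/50 = 33.6 s | 3.6 s | 12% |
| 3 | (1,410 + 360)/50 = 35.4 s | 5.4 s | 18% |

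On the same assumptions in both arms, the difference between arms is distorted by 1.8 × (f in one arm − f in the other) seconds. Equal numbers of failures cancel.

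**Step 4. How many to expect.** The documents give no rate. For assumed failure rates p, the expected number among 50 patients is 50p, and the chance of at least one is 1 − (1 − p)^50:

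- 0.5%: 0.25 expected; 22%
- 1%: 0.5 expected; 39%
- 2%: 1 expected; 64%
- 5%: 2.5 expected; 92%

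Three failures in one arm (6%) is above the expected number at every rate shown, so the last row of the table in Step 3 is an upper illustration.

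**The case against.** The strongest reply is that the passages need not conflict. Eligibility can describe the airway the surgery requires, and the mention of a laryngeal mask can cover what happens when intubation fails. That is a possible reading, but the text does not say so. Nor does it settle the nebulizer's end event or supply a time to intubation for that patient. If the mask is instead a planned airway, eligibility is contradicted, but there is then no failed intubation and no hidden delay.

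Three stronger inferences are tempting, and the documents do not support them.

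- **That the plan excludes failed intubations.** No exclusion rule is written. Leaving these patients out is only the likely default when a t-test meets an undefined value.
- **That time to intubation is the trial's measure of harm from the device.** It is listed as a secondary outcome with no stated purpose.
- **That difficulty with the device would go unseen.** The number of attempts would still register a failed intubation, and a laryngoscopy grade might be recorded too.

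It can also be said that planned mask cases, if enrolled, would be balanced by randomisation and add noise, not bias. That holds if the airway plan is fixed independently of allocation, which the document does not state. The undefined limits of the primary outcome window affect every patient, so they are a wider gap and not one that masks create.

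Finally, the exclusion of predicted difficult airways makes failures uncommon, and failures in both arms would offset each other. Both points stand, and they limit the size of the concern.

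**Conclusion.** The concern holds in a limited form. The airway wording in the Inclusion criteria, the Intubation section and the Secondary outcomes does not line up, and the document does not say what role the laryngeal mask plays. Independently of that wording, time to intubation is conditional on success, and no analysis rule covers a patient in whom it was never achieved. Any resulting bias favours the arm with more such patients.

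Its size cannot be taken from the documents. The 1.8 to 5.4 s range rests on three assumptions: a 30 s mean, failures valued at 120 s, and 1 to 3 failures in one arm with none in the other. It is zero if no failures occur, or if they are equally frequent in both arms on those same values. The likely number is small and power is hardly touched. The case for a change is that the stated definition and test condition a comparison on success, and a better rule costs almost nothing.

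**What to change.** 1. Reconcile the airway terms across the Inclusion criteria, the Intubation section and the Secondary outcomes, and say whether the laryngeal mask is a planned airway or follows failed intubation. Reconcile in the same way the events that end the nebulizer and measurement periods, so that each is defined for every enrolled patient. Which airway plan or end event applies is for the investigators to decide; this review does not choose.
2. State that every randomised patient stays in the assigned arm for analysis, including those never tracheally intubated.
3. Report the number with failed tracheal intubation by arm.
4. Replace the t-test for time to intubation with a rank-based test, such as the Wilcoxon rank-sum test already named for particle counts, placing patients without tracheal intubation at the worst rank.

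The cost is a few sentences and no extra patients. The small downside is that the comparison is by ranks, not means.

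### Baseline particle counts are planned in both arms but not used in the primary analysis; an outside-counter reading taken before device placement could be adjusted for at little cost

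*Combined protocol and SAP*

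**What the plan says.** Under Statistical Methods the primary outcome is particle counts during intubation, to be "compared between groups (device vs no device) using an independent samples t-test (or Wilcoxon Rank Sum Test if distributional assumptions are violated". No covariate is named.

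The Intubation section gives the device-arm steps in this order:

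1. Placement: "one of the study investigators will place the device around" the head.
2. At that point the counters go into position. For the outside one, "one particle counter will be positioned on an IV pole next to the study investigator at the level of his/her nose"; a second sits by the patient's head to sample inside the device.
3. Then the baseline: "The study team will obtain baseline measurements from both inside and outside the device simultaneously".
4. Nebulized saline starts with preoxygenation, and "it will be kept on until after the patient has been intubated".

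The other arm is defined by reference: "For no device group: exactly the same except no device will be placed around" the head. A baseline is therefore planned there too. No reading before placement is described in either arm, and the text does not say which counter supplies the primary outcome.

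Power/sample size, item 1, cites a similar study with an "effect size of 1.0 (20,000 particles vs 12,000, SD of 8,000". Item 2 gives a one-arm precision of +/-2,273 particles, "assuming the box group is 12,000 with a SD of 8,000".

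**The concern.** A baseline value of the outcome variable is often the most useful covariate in a small trial. If room background differs between patients and carries through to the count during intubation, adjusting for it removes that part of the variance. The plan has counters in place and takes a baseline, yet compares the arms without it.

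Timing matters as much. Adjustment is safe for a covariate that treatment cannot have altered. In the device arm the planned reading follows placement, so the device or its handling could have shifted it. An analyst who later added that reading to the model, a natural step once the data exist, could bias the comparison that randomization protects.

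**Working it through.** **Inputs.** From Power/sample size: SD 8,000; means 20,000 and 12,000; 10 and 50 per group; two-sided alpha 0.05. Rho is not in the documents and is assumed to lie between 0 and 0.5. It may be low, because the nebulizer runs during the outcome but not at baseline.

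**The plan's own figures.** With exact t-test power, an effect of 1.35 SD at 10 per group gives 81.4%, and 0.57 SD at 50 per group gives 80.6%. The one-arm half-width is t(0.975, 49) × 8,000/√50 = 2,273.6. All three stated figures reproduce.

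**Half-width for the difference between arms.** With n per group:

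- Unadjusted: t(2n−2) × SD × √(2/n).
- Adjusted for one baseline covariate: t(2n−3) × SD × √[(1−rho²) × (2/n) × (1 + 1/(2n−4))]. The last factor is the expected cost of chance baseline imbalance.

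At n = 50:

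- Unadjusted: 1.9845 × 8,000 × 0.2 = 3,175.
- Adjusted, rho = 0: 1.9847 × 8,000 × 0.2 × √(97/96) = 3,192.
- For other values of rho, multiply 3,192 by √(1−rho²).

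At n = 10:

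- Unadjusted: 2.1009 × 8,000 × √0.2 = 7,516.
- Adjusted, rho = 0: 2.1098 × 8,000 × √0.2 × √(17/16) = 7,781.

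| Assumed rho | 50 per group | Change from 3,175 | 10 per group | Change from 7,516 |
|---|---|---|---|---|
| 0 | 3,192 | +0.5% | 7,781 | +3.5% |
| 0.1 | 3,176 | 0% | 7,742 | +3% |
| 0.3 | 3,045 | −4% | 7,422 | −1% |
| 0.5 | 2,764 | −13% | 6,738 | −10% |

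**Break-even.** Put f = (2n−3)/(2n−4) and k = t(2n−3)/t(2n−2). Adjustment narrows the expected interval when rho exceeds √(1 − 1/(f k²)), which is about 0.10 at 50 per group and 0.26 at 10.

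**Power.** At the cited effect of (20,000 − 12,000)/8,000 = 1.0 SD, unadjusted power is 99.9% at 50 per group, so almost nothing is left to gain. At 10 per group it is 56.2% unadjusted, and 53.4%, 57.3% and 65.6% adjusted at rho 0, 0.3 and 0.5. At 50 per group and the stated detectable effect of 0.57 SD, it is 80.6% unadjusted against 80.2%, 83.7% and 90.0%.

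**Adjusting for the reading as now timed.** If the device moves the outside baseline by s SD and has no effect on the outcome, the adjusted difference is off by about rho × s outcome SDs. With s = 0.25 and rho = 0.5 this is 0.125 × 8,000 = 1,000 particles. In simulations at 50 per group with no true effect (log-normal counts, analysed as logs), the type I error of the adjusted test was 6.5% and 10.9% at rho 0.3 and 0.5 for a 0.25 SD shift, and 11.7% and 27.6% for 0.5 SD. The unadjusted test stayed at 4.9–5.1%. The shifts are assumed; the documents give no information on their size.

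**The case against.** The strongest case for leaving the plan alone is that the planned test is valid, its sizing figures reproduce, and nothing in the documents conflicts. Leaving out a reading taken after placement is also the safe choice. The gain needs a reading that the plan does not describe, so this is a small change to data collection and not simply a better use of data already planned. With rho unknown and perhaps low, the gain may be nil, and at 10 per group adjustment costs precision if rho is below about 0.26. All of this stands, which is why the point is offered only as an improvement. What remains is the asymmetry at 50 per group: a loss of at most 0.5% against a gain of 13% at rho 0.5.

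A reader might infer more in two directions.

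- **That the primary analysis is wrong or the trial underpowered for want of adjustment.** The documents do not support this. Randomization makes the unadjusted comparison valid, and power at the cited effect is over 99% at 50 per group.
- **That adjusted analysis of log counts should become primary.** A mean of 12,000 with SD 8,000 does hint at right skew: a normal distribution would put P(Z < −1.5) = 6.7% of counts below zero. But the documents do not give the shape of the counts, and the plan already has a rank test as fallback. The log scale also replaces the mean difference used for sizing with a ratio of geometric means. If counts are near-symmetric it can lose power: with normal counts truncated at zero (assumed), 50 per group and 0.57 SD, adjusted log analysis had 64%, 67% and 73% power at rho 0, 0.3 and 0.5, against 74% for the t-test. Under skew much of the apparent gain comes from the transform. With log-normal counts at 10 per group, power rises from 62% to 73% from taking logs alone, and the baseline then adds −3, +1 or +8 points.

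**Conclusion.** The point holds as a cheap improvement, not as the correction of an error. Baselines are planned in both arms, the primary analysis ignores them, and the device-arm reading as now timed should not be used as a covariate. A pre-placement outside reading could narrow the interval by about 4% at rho 0.3 and 13% at rho 0.5 with 50 per group (1% and 10% with 10 per group), and would widen it by 0.5% (3.5%) at rho 0. These figures rest on the plan's SD of 8,000, approximate normality, an outcome taken from the outside counter, and assumed values of rho. The gain is possible, not assured. The choice between raw and log scale is a separate trade-off for the sponsor.

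**What to change.** 1. State that the outside, nose-level counter supplies the primary outcome, and name one per-patient summary for the intubation period. Until this is done, rho has no defined meaning.
2. Read that counter's baseline before the device is placed, at a step defined identically for both arms. The no-device arm has no placement to mark the moment, so the step must be written out.
3. Prespecify the primary comparison as an ANCOVA of the outside-counter outcome on arm and this baseline, with a 95% confidence interval. Keep the planned unadjusted t-test or Wilcoxon test as a sensitivity analysis.
4. Do not adjust for the inside reading or for any reading taken after placement. If the outside reading cannot be moved, keep the unadjusted test as primary.
5. Fix the scale in advance. The log scale helps if counts are right-skewed, but it makes the effect a ratio and needs a rule for zero counts.

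The cost is a few sentences in the SAP and one reading moved earlier on a counter already in the room, with no new equipment or patients. The statistical downside is the small precision loss if rho is near zero.
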